					imputation rules of the main estimator, that is, the multiple imputation method (MI) will be used to impute the missing data in the placebo group, and the J2R (jump to reference) method will be used to impute the missing data in the CBP-201 group.
Estimand of key secondary endpoints	
The differences in the following measures in patients aged 12 years and older with moderate to severe AD and weighing ≥ 40 kg between the CBP-201 300mg Q2W group and the placebo group:
 
 • The proportion of subjects achieving EASI-75 at W16; • The proportion of subjects whose weekly average PP-NRS is decreased by ≥ 4 points from baseline at W16; • The proportion of subjects whose weekly average PP-NRS is decreased by ≥ 3 points from baseline at W16; • Change and percentage change in the weekly 	FAS (will include all subjects in Randomization Set 1 who have received the study drug at least once.)	
For subjects who experience intercurrent events, their visits after the intercurrent events will be handled in accordance with the strategies for managing intercurrent events listed in Table 12.1 and Table 12.3.
 
If the target variable is still missing after application of the strategies for managing intercurrent events, the multiple imputation (MI) method will be used to impute the missing data in the placebo group, and the J2R (jump to reference) method will be used to impute the
	
For categorical variables, differences in response rates between the treatment group and placebo group and their 95% confidence intervals will be analyzed using the Cochran-Mantel-Haenszel test stratified by baseline disease severity (IGA 3 or 4).
 
For continuous variables, analysis will be performed using an MMRM model that will include treatment group, baseline disease severity (IGA 3 or 4), baseline value of the corresponding endpoint, visit, interaction of visit and treatment group, and the LSMEAN estimate values and their 95% confidence
	
Sensitivity analysis 1: When the target variable is still missing after application of the strategy for managing intercurrent events, categorical variables will be classified as treatment failure. Continuous variables should be imputed with WOCF.
 
Supplementary Analysis 1: Primary analysis will be performed using the PPS.
 
Supplementary analysis 2: The treatment policy strategy will be used for all intercurrent events; the FAS will be used, and the missing data will be subject to the imputation rules of the main

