4.1.2. Secondary endpoints

Key secondary endpoints

- The proportion of subjects achieving EASI-75 at W16;
- The proportion of subjects whose weekly average PP-NRS is decreased by ≥ 4 points from baseline at W16;
- The proportion of subjects whose weekly average PP-NRS is decreased by ≥ 3 points from baseline at W16;
- Change and percentage change in the weekly average PP-NRS from baseline at W16;
- The proportion of subjects achieving EASI-90 at W16.

Other secondary endpoints

- Change and percentage change in the EASI score from baseline at W16;
- The proportion of subjects achieving EASI-50 at W16;
- Percentage change in the BSA of AD involvement from baseline at W16;
- Percentage change in the SCORAD score from baseline at W16;
- Change in DLQI from baseline at W16;
- Change in POEM from baseline at W16;
- Percentage change in the weekly average PP-NRS from baseline at W2;

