Estimand of key secondary endpoints	
The differences in the following measures in patients aged 12 years and older with moderate to severe AD and weighing ≥ 40 kg between the CBP-201 300mg Q2W group and the placebo group:
 
 • The proportion of subjects achieving EASI-75 at W16 • The proportion of subjects whose weekly average PP-NRS is decreased by ≥ 4 points from baseline at W16; • The proportion of subjects whose weekly average PP-NRS is decreased by ≥ 3 points from baseline at W16; 	FAS1 (will include all subjects in RS1 who have received the study drug at least once).	
For subjects who experience intercurrent events, their visits after the intercurrent events will be handled in accordance with the strategies for managing intercurrent events listed in Table 7.4.2.
 
If the target variable is still missing after application of the strategies for managing intercurrent events, the multiple imputation (MI) method will be used to impute the missing data in the placebo group, and the J2R (jump to reference)
	
For categorical variables, differences in response rates between the treatment group and placebo group and their 95% confidence intervals will be analyzed using the Cochran-Mantel-Haenszel test stratified by baseline disease severity (IGA 3 or 4).
 
For continuous variables, analysis will be performed using an MMRM model that will include treatment group, baseline disease severity (IGA 3 or 4), baseline value of the
	
Sensitivity analysis 1: When the target variable is still missing after application of the strategy for managing intercurrent events, categorical variables will be classified as treatment failure. Continuous variables should be imputed with WOCF.
 
Sensitivity analysis 2: For the subjects who are incorrectly stratified and randomized, the analysis will be performed using the stratification during randomization and the method the same as the main estimator;
 
Supplementary analysis 1: The analysis will be performed using the same method as the main estimand based on the PPS1.
 
Supplementary analysis 2: The treatment policy strategy will be used for all intercurrent events; the FAS1 will be used,

Label of estimand	Description of estimand	Main estimator			Sensitivity/ Supplementary analysis
		Analysis sets	Rules for imputation	Model/method for the main analytical methods	

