	
 Change and percentage change in the weekly average PP-NRS from baseline at W16; The proportion of subjects achieving EASI-90 at W16 
A patient should be regarded as treatment failure if he/she uses prohibited drugs/treatments specified in the protocol for which the study treatment must be early terminated or other rescue therapy that has a major impact on the assessment of the key secondary endpoints due to poor response, or has premature discontinuation of treatment/EOT due to AEs. In this case, continuous variables should be imputed with WOCF.
		method will be used to impute the missing data in the CBP- 201 group.	corresponding endpoint, visit, interaction of visit and treatment group, and the LSMEAN estimate values and their 95% confidence intervals will be summarized.	and the missing data will be subject to the imputation rules of the main estimator, that is, the multiple imputation method (MI) will be used to impute the missing data in the placebo group, and the J2R (jump to reference) method will be used to impute the missing data in the test group.

In the J2R (jump to reference) method, when the data of subjects of the active treatment group are missing, it is assumed that their statistical results are the same as those of the placebo group, that is, it is considered that the pharmacological action of the drug for the active treatment group is the same as that of the placebo group. PROC MI will be used for J2R imputation, and the missing data of the active treatment group will be imputed with the results obtained by posterior predictive distribution of the placebo group. Markov Chain Monte Carlo (MCMC) will be used to extend the data, and a regression method will be used to generate M datasets (M is set as 30 for the primary analysis and as 1000 for other cases in this study). The imputed variables should include: treatment group, stratification factor (severity of baseline disease), baseline value of corresponding endpoint and measurement at each visit. Random seed is the earliest date of the first dose to all subjects.

Table 5 Random Seeds of Multiple Imputation

Endpoints	Random Seeds
IGA	Minimum date of the first dose
EASI	Minimum date of the first dose + 1
PP-NRS	Minimum date of the first dose + 2
BSA	Minimum date of the first dose + 3
SCORAD	Minimum date of the first dose + 4
DLQI	Minimum date of the first dose + 5
POEM	Minimum date of the first dose + 6

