7.4.4. Other efficacy endpoint analysis

The categorical efficacy endpoint analysis in Stage 1 will be performed using the same method as the primary efficacy endpoint analysis.

The continuous efficacy endpoint analysis in Stage 1 will be performed using the same method as the secondary efficacy endpoint analysis.

According to the investigator's judgment, AD aggravation or deterioration of symptoms which requires drugs or treatments originally prohibited by the protocol for rescue therapy will be defined as "AD recurrence" event.

The number of AD recurrence, the number of subjects with AD recurrence, and the number of days of AD recurrence in Stage 1, from baseline to W8, from W9 to W16 will be analyzed. The total number of AD recurrence in each stage will be summarized. AD recurrence will be summarized by the number of recurrences, that is, 0, 1, 2 and ≥ 3 . The number and percentage of subjects will be calculated. Chi-squared test will be adopted to compare whether the differences between the two groups are statistically significant. The total number of subjects with AD recurrence in each stage will be summarized, and the number and percentage of subjects will be calculated. Chi-squared test will be performed to compare whether the differences between the two groups are statistically significant. The number of days of AD recurrence in each stage will be summarized by descriptive statistics.

7.4.5. Efficacy analysis in stage 2

During efficacy analysis in Stage 2, the percentage of subjects achieving efficacy endpoint and its confidence interval will be calculated for categorical efficacy endpoints. For continuous efficacy endpoints, ANCOVA model will be used to calculate the mean, the Least Square Mean, 95% confidence interval and SE of the change from baseline and percentage change from baseline of each efficacy endpoint. The model will include treatment group, severity of baseline disease (IGA 3 or 4), and baseline value of corresponding endpoint. Inferential statistics will not be performed during the Stage 2 analysis. The following two analyses will be performed.

Analysis method 1: Categorical efficacy endpoints after the occurrence of events will be regarded as no response for subjects who have the following conditions; continuous efficacy endpoints after the occurrence of events will be imputed using WOCF in Stage 2; other missing data except for the conditions above will be imputed using multiple imputation (MI).

- Group adjustment

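### The Stage 1 MMRM applies one baseline slope and one severity effect to every visit; if the slope differs by visit, the W16 difference stays unbiased but loses some precision

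*SAP*

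**What the plan says.** In the later SAP, section 7.4.3, the model is set out as follows: "analysis will be performed using an MMRM model that will include treatment group, baseline disease severity (IGA 3 or 4), baseline value of the". It then names what is left of the model, "corresponding endpoint, visit, interaction of visit and treatment group", with least-squares means and 95% intervals to be reported. Protocol Table 12.4 (section 12.7.3) has the same list, including "baseline value of the corresponding endpoint, visit, interaction of visit and treatment group", and SAP v1.0 section 7.4.3 repeats it. Treatment may vary by visit; baseline and severity may not. None of the three texts names a covariance structure, a degrees-of-freedom method or the visits that enter the model.

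The model serves one key secondary item, "Change and percentage change in the weekly average PP-NRS from baseline at W16", which is fourth of five in the fixed sequence. Section 7.4.4 extends it to the rest: "The continuous efficacy endpoint analysis in Stage 1 will be performed using the same method as the secondary efficacy endpoint analysis".

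Two other models in the SAP are less restrictive or may be:

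- **Imputation model (7.4.3):** "The imputed variables should include: treatment group, stratification factor (severity of baseline disease), baseline value of corresponding endpoint and measurement at each visit".
- **Stage 2 ANCOVA (7.4.5):** "The model will include treatment group, severity of baseline disease (IGA 3 or 4), and baseline value of corresponding endpoint". It has no visit term; if fitted visit by visit, as the by-visit Stage 2 endpoints suggest, it gives each visit its own slope.

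**The concern.** Change from baseline commonly depends only weakly on baseline soon after the first dose. It may depend more strongly later, when patients who started high have had room to fall. Entry floors (EASI at least 16, PP-NRS at least 4) make that pattern plausible here. A single fitted slope is a weighted average over visits, and the early visits, which usually have the smaller residual variance, tend to dominate it. If the W16 slope is steeper, the W16 comparison is then corrected for only part of any chance baseline difference between arms, and the uncorrected part stays in the residual variance.

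What is at stake is precision. The W16 interval for PP-NRS change, and for EASI, DLQI and POEM change, could be wider than the collected data require. PP-NRS change also gates the EASI-90 test, so lost precision there carries one step further.

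**Working it through.** **The plan's own figure.** The documents give no SD, slope, correlation or interval width for any MMRM endpoint. The only reproducible figure is the primary-endpoint power (protocol 12.3): 27% v 9%, 144 v 72 completers, two-sided 0.05. The pooled rate is (144×0.27 + 72×0.09)/216 = 0.21. The null SE is √(0.21×0.79×(1/144+1/72)) = 0.0588 and the alternative SE is √(0.27×0.73/144 + 0.09×0.91/72) = 0.0501. Then z = (0.18 − 1.96×0.0588)/0.0501 = 1.29, giving power 0.902. The stated 90% reproduces, and it does not depend on the MMRM.

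**Formula for the loss.** With complete data and an unstructured covariance, in large samples:

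- W16 variance ratio (plan's model / visit-specific slopes) = 1 + (b16 − bc)² × var(baseline) / (residual variance at W16)
- bc = (1′Σ⁻¹b)/(1′Σ⁻¹1), the common slope, where b is the vector of visit slopes and Σ the residual covariance.

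**EASI change.** There are five scheduled assessments (W2, W4, W8, W12, W16; protocol Table 1.1). Assumed, not in the documents: baseline SD 11, residual SD rising from 6 to 9.5, residual AR(1) correlation 0.5–0.7, slopes and SDs changing in equal steps per visit.

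- Slopes −0.25 to −0.60, correlation 0.5: bc = −0.363; ratio = 1 + 0.237² × 121/90.25 = 1.075.
- Same slopes, correlation 0.7: bc = −0.338; ratio = 1 + 0.262² × 1.341 = 1.092.
- Simulation of this case (1,500 trials, 170 v 85): 1.06–1.10.
- Flatter slopes (−0.35 to −0.50): 1.01–1.03. Steeper (−0.15 to −0.75): 1.22–1.27. Equal slopes: 0.99–1.00.

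An 8% excess is worth 255 × (1 − 1/1.08) = 19 subjects, or √1.08 = 1.039, an interval about 4% wider.

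**PP-NRS.** Simulation of 300 trials per scenario, complete data, both models fitted to each trial. Assumed: baseline mean 7 and SD 1.7 before clipping to 4–10, follow-up SD 1.8–2.4, true W16 difference −1.5. Unless stated, 170 v 85, eight two-weekly visits and residual correlation 0.85. The last column is 1/(SE ratio)² − 1.

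| Scenario | Slope of change, W2 and W16 | SE ratio, interaction / plan | Excess variance under the plan |
|---|---|---|---|
| Equal slopes | −0.48, −0.48 | 1.0033 | −0.7% |
| Mild | −0.33, −0.46 | 1.0009 | −0.2% |
| Moderate | −0.26, −0.58 | 0.9869 | 2.7% |
| Moderate, 144 v 72 | −0.26, −0.58 | 0.9865 | 2.8% |
| Moderate, correlation 0.6 | −0.26, −0.58 | 0.9921 | 1.6% |
| Moderate, five visits | −0.26, −0.58 | 0.9809 | 3.9% |
| Moderate, severity effect growing 0.1 to 0.8 | −0.26, −0.58 | 0.9784 | 4.5% |
| Strong | −0.10, −0.86 | 0.8993 | 23.6% |
| Moderate, percentage change | −0.26, −0.58 (absolute scale) | 1.0026 | −0.5% |

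In the moderate case the fitted common slope was −0.31 against a true W16 slope of −0.58, so the pull towards early visits is real when slopes diverge. In every absolute-change scenario the two models gave the same mean W16 difference to within 0.01 points, with coverage of about 93–97% for both.

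**Cost in parameters.** Two added interactions take 2 × (visits − 1) terms: 8 with five visits, 14 with eight.

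**The case against.** Main-effect covariates in a prespecified MMRM are a legitimate choice, and the same model stands in the protocol and both SAP versions. The gain rests wholly on slopes the documents do not report. The larger figures belong to EASI change, which lies outside the fixed sequence. Percentage change, half of the only key secondary item that uses this model, gains nothing in the scenario run. The simulations use complete data, so they do not show the added uncertainty from imputation. The pull towards early visits depends on a covariance structure that the SAP leaves unstated, arguably a firmer gap than the missing interactions. All of this stands, and it limits the point to an optional precision improvement.

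A reader might infer more than the documents support:

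- **That W16 estimates are biased.** Under randomisation they are not, and the simulations show none.
- **That they are under-adjusted as a matter of fact.** That holds only if slopes differ by visit; no document says they do.
- **That the added terms must tighten the intervals.** With equal slopes the interval was slightly wider in 95% of simulated trials.
- **That the change is free.** SAP v1.0 is dated 20 September 2022, the day after the blinded review for the primary analysis. The later SAP already cites a final-analysis review on 18 October 2023. Protocol 6.3.2 and 12.5 have W16 data unblinded at the primary analysis. The unblinding date is not given, but this sequence suggests it had passed. Replacing the main model of a fixed-sequence endpoint at that stage would be post hoc.

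**Conclusion.** The point holds as a conditional, minor improvement. As written, the Stage 1 MMRM gives baseline and severity one effect across all visits. If slopes diverge, the W16 difference is unbiased but less precise than the data allow. Under the assumed inputs the excess variance is about 1.6–4.5% for absolute PP-NRS change in moderate scenarios (about 24% only with extreme divergence). For EASI change it is about 7–9%, with a range of roughly 1–27%. It is about nil for percentage change (simulated for PP-NRS only) and for equal or nearly equal slopes.

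The trade is asymmetric: the largest SE penalty from adding the terms was about 0.3%, the largest gain in the PP-NRS runs about 10%. The primary endpoint (stratified CMH) and the sample size are untouched. The figures rest on assumed SDs, slopes and correlations, complete data and an unstructured covariance. That all visits from W2 to W16 enter the model is inferred from the visit schedule.

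**What to change.** In SAP 7.4.3, and in protocol Table 12.4 for consistency, add baseline-by-visit and severity-by-visit terms to the MMRM for all continuous Stage 1 endpoints. State an unstructured covariance, the degrees-of-freedom method and the visits included.

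Make this the main model only if W16 data are still blinded. If they are not, keep the prespecified model for the fixed sequence and report the interaction model as a labelled sensitivity analysis; it could also be run in the supplementary analysis that includes the 75 later subjects.

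The cost is a line or two of text and code, 8–14 extra parameters, and an SE about 0.3% larger if slopes are in fact equal. No new data are needed.

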- DLQI: It is a questionnaire containing 10 items to assess the impact of AD on quality of life (QOL) in the past week, and the scores range from 0 (no disease) to 30 (severe disease); the higher the score, the worse the quality of life. Refer to [Section 17.2, Appendix B](#). DLQI score will only be assessed among subjects ≥ 16 years, and it will be assessed once a week during the study period.
- POEM: It is a questionnaire composed of 7 items to assess disease symptoms on a scale of 0-4 (dryness, itching, flaking off, cracking, sleeplessness, bleeding and weeping or oozing); the scores range from 0 (no disease) to 28 (severe disease); the higher the score, the worse the quality of life. Refer to [Section 17.3, Appendix C](#). It will be assessed once a week during the study period.

2) Investigator's efficacy assessments (completed by the investigator):

- IGA: The Validated Investigator Global Assessment for AD (vIGA-AD™) Scale is a 5-point classification scale based on the overall appearance of the skin lesions at a specific time point (0=clear; 1=almost clear; 2=mild; 3=moderate; 4=severe). It should be noted that in order to be eligible for selection, the IGA score must be ≥ 3 . See [Section 17.4, Appendix D](#). Please also note that IGA-1 should not contain scales.
- EASI: The EASI scale quantifies the severity and extent of AD, as well as the severity of erythema, infiltration, excoriation and lichenification of the four anatomical regions—head and neck, trunk, upper extremities and lower extremities. The total EASI score ranges from 0 (lowest) to 72 (highest); the higher the score, the higher the severity of AD (more severe). It should be noted that in order to be eligible for selection, the EAS score must be ≥ 16 . See [Section 17.5, Appendix E](#).
- The “Rule of Nines” is used to estimate the maximum percentage of AD-affected BSA in each area: head and neck [9%], anterior trunk [18%], back [18%], upper limbs [18%], lower limbs [36%] and genitals [1%]. The number of palms of AD-affected skin in a body part can be used to determine the extent (%) of AD involvement in that body part. Regardless of the age of the subject, the area of the subject's entire palm (five fingers adducted together) is about 1% of the subject's

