12.3. Basis of Sample Size

The sample size of 255 cases (in a 2:1 ratio, 170 cases in the CBP-201 300 mg Q2W group, and 85 cases in the placebo group. Assuming that the dropout rate in the treatment group is 15%, then about 144 cases in the CBP-201 300 mg Q2W group and 72 cases in the placebo group will be able to complete the study) can provide a power of 90% to detect the therapeutic effect on the primary endpoint in the CBP-201 300 mg Q2W group and the placebo group. This power is calculated based on the following assumption: the proportion of subjects reaching the primary efficacy endpoint is 27% in the CBP-201 300 mg Q2W group and 9% in the placebo group, and the significance level for two-sided tests is 0.05.

Based on the results of another conducted phase II international multicenter clinical study of CBP-201 in patients with moderate-to-severe atopic dermatitis, the proportion of subjects reaching the primary efficacy endpoint was 28.1% in the CBP-201 300mg Q2W group and 10.7% in the placebo group, at a two-sided test significance level of 0.05, and if the results of this trial are similar to that of the WW001 trial, the above sample size would provide a power of more than 85% to detect the therapeutic effect on the primary endpoint between the CBP-201 300 mg Q2W group and the placebo group. Therefore, no adjustment is made to the sample size.

The primary analysis of this study will still be based on the 255 subjects enrolled in accordance with V2.1 and its earlier versions of the protocol. Subjects newly enrolled (approximately 81 cases) based on the protocol after V2.1 will not be included in the primary analysis, and only supplementary analysis will be performed.

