7.4.3. Analysis of the primary efficacy endpoint and key secondary efficacy endpoints

Label of estimand	Description of estimand	Main estimator			Sensitivity/ Supplementary analysis
		Analysis sets	Rules for imputation	Model/method for the main analytical methods	
Estimand of primary endpoint	
The difference in efficacy in patients aged 12 years and older with moderate to severe AD and weighing > 40 kg between the CBP-201 300 mg Q2W group and placebo group.
 
A patient is considered as treatment success if the patient has an IGA score of 0-1 which is decreased by ≥ 2 points from baseline at W16.
 
A patient should be regarded as treatment failure if he/she uses prohibited drugs/treatments specified in the protocol for which the study treatment must be early terminated or other rescue therapy that has a major impact on the assessment of the primary endpoint due to poor response, or has premature discontinuation of treatment/EOT due to AEs.
	FAS1 (will include all subjects in RS1 who have received the study drug at least once).	
For subjects who experience intercurrent events, their visits after the intercurrent events will be handled in accordance with the strategies for managing intercurrent events listed in Table 7.4.2.
 
If the target variable is still missing after application of the strategies for managing intercurrent events, the multiple imputation (MI) method will be used to impute the missing data in the placebo group, and the J2R (jump to reference) method will be used to impute the missing data in the CBP- 201 group.
	
Differences in response rates between the treatment group and placebo group and their 95% confidence intervals will be analyzed using the Cochran-Mantel-Haenszel test stratified by baseline disease severity (IGA 3 or 4). The Type I error level for statistical significance of the difference in response rates between CBP-201 and placebo is set at 0.05 (two-sided test).
	
Sensitivity analysis 1: When the target variable is still missing after application of the strategy for managing intercurrent events, it will be classified as treatment failure.
 
Sensitivity analysis 2: When the target variable is still missing after application of the strategy for managing intercurrent events, tipping point analysis will be used for analysis.
 
Sensitivity analysis 3: For the subjects who are incorrectly stratified and randomized, the analysis will be performed using the stratification during randomization and the same method as the main estimand;
 
Supplementary analysis 1: The analysis will be performed using the same method as the main estimand based on the PPS1.
 
Supplementary analysis 2: The treatment policy strategy will be used for all intercurrent events; the FAS1 will be used,

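### The five-grade IGA is imputed with a normal-theory model and no rounding or ordinal step, so applied as written the imputed response is about 2-4% against an assumed placebo rate of 9%

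*SAP*

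**What the plan says.** Protocol 6.2 describes the vIGA-AD, which "is a 5-point classification scale based on the overall appearance of the skin lesions at a specific time point", with whole grades from 0 (clear) to 4 (severe). Entry requires a grade of 3 or 4.

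The SAP 7.4.3 estimand table states: "A patient is considered as treatment success if the patient has an IGA score of 0-1", with the further condition of a fall of at least 2 points from baseline at W16.

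For data still missing after the intercurrent-event strategies, the placebo arm is handled by multiple imputation and the CBP-201 arm by jump to reference. The same section says that PROC MI will be used, that "Markov Chain Monte Carlo (MCMC) will be used to extend the data", and that "a regression method will be used to generate M datasets". The imputed variables include the measurement at each visit, and Table 5 gives IGA its own random seed. It is therefore the IGA score that is imputed, not the response.

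Both SAP versions contain this paragraph. Protocol Table 12.4 leaves the detailed method to the SAP. Neither document gives a rounding step, bounds, a cut-off or an ordinal model for imputed IGA.

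**The concern.** In PROC MI, MCMC and the regression method are normal-theory procedures for continuous variables. Applied to a five-grade scale they return values such as 1.3, which then have to be classed as success or failure.

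On the written two-part rule, 1.3 fails in both randomization strata. From baseline 3 it is a fall of only 3 - 1.3 = 1.7. From baseline 4 the fall is large enough, but 1.3 is outside 0-1. Yet the nearest grade to 1.3 is 1, almost clear, which is a success.

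This conflicts with the SAP's own premise for jump to reference, that subjects with missing data in the active arm behave like placebo subjects. It also touches more than dropout, because intercurrent events 5 and 6 discard observed values and use the same imputation. Two programmers who handle the draws differently would report different primary estimates.

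**Working it through.** **1. The plan's own figure.** Protocol 12.3 says the sample "can provide a power of 90% to detect the therapeutic effect on the primary endpoint", with "in a 2:1 ratio, 170 cases in the CBP-201 300 mg Q2W group, and 85 cases in the placebo group", about 144 and 72 completing after 15% dropout, 27% v 9% response, and two-sided 0.05.

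- Pooled rate = (72 × 0.09 + 144 × 0.27)/216 = 0.21.
- SE under H0 = √[0.21 × 0.79 × (1/72 + 1/144)] = 0.0588.
- SE under H1 = √[0.27 × 0.73/144 + 0.09 × 0.91/72] = 0.0501.
- Power = Φ[(0.18 - 1.96 × 0.0588)/0.0501] = 90.2%.

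The stated 90% is reproduced. No imputed value enters this calculation.

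**2. Imputed response among missing subjects.** The documents give no W16 IGA distribution. I assume three for placebo, each with the protocol's 9% at grade 0-1, and approximate the imputation draws by a normal distribution with the same mean and SD. Because entry needs a grade of 3 or 4, the two-part rule without rounding amounts to a draw of 1 or less. With rounding, it amounts to a draw below 1.5.

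| Assumed P(IGA = 0, 1, 2, 3, 4) | Mean | SD | Unrounded: Φ[(1 - mean)/SD] | Rounded: Φ[(1.5 - mean)/SD] | Between 1 and 1.5 |
|---|---|---|---|---|---|
| A: .02, .07, .21, .45, .25 | 2.84 | 0.95 | 2.6% | 7.8% | 5.2% |
| B: .01, .08, .16, .40, .35 | 3.00 | 0.96 | 1.9% | 5.9% | 4.0% |
| C: .03, .06, .31, .45, .15 | 2.63 | 0.91 | 3.7% | 10.8% | 7.1% |

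Negative draws make up 0.1-0.2%. Excluding them lowers the unrounded range only to 1.8-3.5%.

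**3. Equal missingness, 15% per arm.** Let q be the unrounded imputed response.

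- Placebo rate = 0.85 × 9% + 0.15 × q = 7.9-8.2%, against 9.0% if q were 9%. The fall is 0.15 × (9 - 3.7) = 0.8 to 0.15 × (9 - 1.9) = 1.1 points.
- CBP-201 rate = 0.85 × 27% + 0.15 × q = 23.2-23.5%, against 24.3%. The fall is the same.
- Difference = 0.85 × 18 = 15.3 points in every case, because both arms draw from the placebo distribution.

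**4. Unequal missingness (assumed).** Shift in the difference = (m_CBP - m_placebo) × (q - 9%).

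- Placebo 20%, CBP-201 10%: (-0.10) × (3.7 - 9) = +0.5 to (-0.10) × (1.9 - 9) = +0.7 points.
- Placebo 25%, CBP-201 10%: (-0.15) × (3.7 - 9) = +0.8 to (-0.15) × (1.9 - 9) = +1.1 points.
- If CBP-201 is the arm with more missing data, the sizes are the same and the sign reverses.

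For scale, the SE of the planned 18-point difference with 170 and 85 subjects is √[0.27 × 0.73/170 + 0.09 × 0.91/85] = 4.6 points. The shift is therefore about 0.1-0.2 SE.

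**The case against.** The strongest reply is that the SAP is silent rather than wrong: it never says that a fractional draw is a failure, and a programmer may well round. With rounding, the imputed response is 5.9-10.8%, on either side of 9%. That stands as a limit on the claim. However, rounding is a step the SAP does not contain, and without it the written rule rejects draws between 1 and 1.5.

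A reader might go further and infer that fractional and negative draws all fail, and that the primary analysis is therefore biased towards CBP-201. The documents do not support this. Fractions between 0 and 1 satisfy the rule. Negative draws are negligible and pass if 0-1 is read as 1 or less. The treatment difference does not move when missingness is equal, and it moves against CBP-201 if that arm has more missing data.

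The amount imputed may also be modest. Rescue for poor response and discontinuation for adverse events are already set to non-response, so, apart from events 5 and 6, the imputed share should be below total dropout.

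The SAP also has two checks that do not use imputed IGA scores. Sensitivity analysis 1 counts remaining missing values as failures, and the tipping point analysis varies binary response from 0 to 100% in each arm. Together they bound the effect on the conclusion. They do not correct the primary estimate, and agreement with sensitivity analysis 1 says little when unrounded imputation is already close to failure for all. On a literal reading, both cover only values still missing after the strategies, so subjects imputed under events 5 and 6 may lie outside them.

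**Conclusion.** The point holds as a defect in the main estimator of the primary endpoint, modest in size. Applied as written, SAP 7.4.3 gives missing subjects a response of about 2-4% where the placebo rate is assumed to be 9%; rounding would give about 6-11%. At 15% missing in both arms, both rates are about 0.8-1.1 points too low and the difference is unchanged. With 20-25% v 10% missing, the difference moves by about 0.5-1.1 points, in a direction set by which arm has more missing data.

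These sizes rest on assumed IGA distributions, a normal approximation to the imputation draws and assumed missingness. The 9%, 27% and 15% are the protocol's planning values. Sample size and stated power are unaffected. The change is worth making because the primary estimate should not depend on an unstated step.

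**What to change.** For IGA only, replace MCMC plus regression in SAP 7.4.3 with an ordinal logistic imputation model, or a binary logistic model for response. Fit the reference step on placebo observations and combine grades 0 and 1 if they are sparse. Keep the present method for EASI, PP-NRS and the other continuous scores.

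At minimum, add one sentence: imputed IGA values are rounded to the nearest grade within 0-4 before both parts of the success rule are applied.

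Protocol 6.3.2 provides for unblinding Stage 1 once the 255 subjects complete it, and the later SAP refers to a data review in October 2023. If Stage 1 is already unblinded when the SAP is changed, keep the pre-specified analysis and report the new one beside it as a labelled sensitivity analysis.

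The cost is SAP wording and a small program change. The main drawback is sparse data: 9% of 72-85 placebo subjects is only about 6-8 responders, which limits any ordinal model fitted on that arm.
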